10.3.5 Microbial Sample Collection / Scrub Cup Technique

Quantitative cultures (treatment baselines and post treatment application) will be obtained by a modification of the cylinder sampling technique of Williamson-Kligman scrub cup technique. To collect the samples, a sterile scrub cup (inner skin surface area of 3.46 cm²) will be placed on the site and held firmly to the skin. Sampling solution (SS) (3.0 mL) will be pipetted into the cup and the skin will be massaged in a sweeping manner for one minute using a sterile rubber policeman. Using a sterile transfer pipette, the SS will be removed and placed in a sterile test tube. An additional 3.0 mL of fresh SS will be pipetted into the cup and the scrub procedure will be repeated. This solution will be pooled with the first solution collected.

Sampling Solution (SS)

Bacterial Enumeration Methods

Following sample collection, 10-fold serial dilutions (1 mL sample + 9 mL PBW) will be prepared using Butterfield's phosphate buffered water (PBW). One-mL aliquots of appropriate dilutions will be pour-plated in duplicate using trypticase soy agar containing neutralizers (TSA+). Duplicate plating of sample dilutions, according to the method described in ASTM E1173-15, is considered adequate for the objectives of this phase 2 clinical evaluation. Samples must be plated within 30 minutes of collection. After 72 ± 4 hours of aerobic incubation at 30 ± 2C, colonies will be counted and viable cells in the original sample will be calculated according to Standard Operating Procedures. After incubation, plates may be refrigerated up to 48 hours prior to counting.

Raw colony counts from each dilution will be recorded on the appropriate CRFs for each subject. The average CFU/cm² of skin will be calculated using a validated Excel spreadsheet using this formula: CFU/cm² = Average CFU/mL x 6 mL/3.46 cm². The average number of microorganisms recovered (CFU/cm²) of skin for the treatment day baseline samples will be calculated using the formula to convert the volume of sample collected into CFU/cm² of skin:

$$R = \log_{10} \left[\frac{F \left(\frac{\sum_{i=1}^2 c_i}{n} \right) D}{A} \right]$$

Where: R = the average CFU count in log₁₀ scale per cm² of skin.

F = total mL of sampling solution (SS) added to the sampling cylinder (6 mL);

$\frac{\sum_{i=1}^2 c_i}{n}$ = average of the duplicate colony counts used for each sample collected

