D = Dilution factor of the plates counted. One of 10^0 , 10^1 , 10^2 , 10^3 , 10^4 , or 10^5 .
 A = Inside area of the sampling cylinder (3.46 cm^2)

The average CFU/mL, CFU/cm², and log₁₀ CFU/cm² will be calculated for samples from each test site in the same manner.

In order to avoid potential calculation problems due to taking the logarithm of zero, counts of less than 1 CFU/cm² will be treated as 1 CFU/cm², such that the log₁₀ transformation is no less than zero.

Neutralizer Validation

The effectiveness of the neutralizer system must be validated prior to the study start date to demonstrate that the antimicrobial is effectively neutralized and there is no effect on the growth of microorganisms. A procedure that will include *in-vivo* sampling will be combined with an *in-vitro* evaluation using procedures in accordance with ASTM E1054-08(2013).¹² The procedure is in Appendix 22.8. Two organisms, Methicillin-resistant *Staphylococcus epidermidis* (MRSE), ATCC 51625 and Methicillin-sensitive *Staphylococcus epidermidis* (MSSE), ATCC 12228, will be evaluated. These data will be provided in the final report.

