- After the test area is marked, the area will be processed using three 70% isopropyl alcohol swabs for a total of one minute to prepare the site; the area will be allowed to dry. This step is to prepare the skin for the neutralization test.
- Prep the test area with the Test Article according to the instructions provided in Appendix 22.7.
- Using the scrub cup technique at approximately 10-minutes post-prep, begin collecting samples from the site using SS. This technique is described in the Protocol.
- The procedure is repeated on the other side of the body with the Test Article.

5. *In-vitro* Test Procedures [performed using the collected samples in accordance with ASTM E1054-08(2013)]

Inoculum Preparation:

Two days prior to beginning the neutralization assay, *S. epidermidis* MRSE (ATCC #51625) or *S. epidermidis* (ATCC #12228) from a stock culture slant, lyophilized vial, or cryogenic stock culture will be transferred into a tube containing Tryptic Soy Broth (TSB). The tube will be incubated for 24 hours \pm 4 hours at 30 °C \pm 2 °C.

One day prior to beginning the neutralization assay, loopfuls of the broth culture will be streaked onto Tryptic Soy Agar (TSA) plates, and the plates will be incubated for 24 hours \pm 4 hours at 30 °C \pm 2 °C.

Immediately prior to initiating the neutralization assay, an inoculum suspension will be prepared in Phosphate Buffer Saline (PBS) solution from the culture on an agar plate, and the concentration adjusted to approximately 1.5×10^8 to 5.0×10^8 CFU/mL. The suspension will then be serially diluted in PBS to achieve an inoculum titer of approximately 1.5×10^3 to 5.0×10^3 CFU/mL, and used as test inoculum. .

(note – the reference to test article applies to all treatment materials; all procedures outlined, where applicable, will employ all treatment materials.)

Neutralizer effectiveness (Test 1):

- a. Out of the 6.0 mL aliquot of SS taken from the volunteer, 4.90 mL will be transferred to a new sterile tube and inoculated with 0.1 mL aliquot of the challenge microorganism so that the resulting suspension contains approximately 30 – 100 colony-forming units (CFU) /mL of the challenge microorganism).
- b. Within one minute after the addition of the challenge microorganism, the microorganisms will be enumerated by standard microbiological methods extant in the laboratory.
- c. Duplicate one mL aliquots will be removed and plated using TSA pour plates.

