- e. Duplicate one mL aliquots will be removed and plated using TSA pour plates.
- f. This procedure will be repeated an additional three times for a total of four replicates for each test organism.

Incubation:

All plates for Tests 1, 2, 3 and 4 will be incubated for 48 ± 4 hours at $35^\circ \pm 2^\circ\text{C}$.

Interpretation of data:

- a. The number of surviving challenge microorganisms for each replicate from each test will be average count of the duplicate plates.
- b. The number of survivor values will be transformed to \log_{10} .
- c. The number of survivors (\log_{10}) from each Test (1, 2, and 4) will be compared to the test microorganism viability population (Test 3).
- d. Neutralization aspects of the SS will be considered adequate if the mean \log_{10} CFU/mL of Test 1 is not more than 0.20 \log_{10} less than the mean \log_{10} CFU/mL of Test 3 (Mean \log_{10} CFU/mL from Test 3 – Mean \log_{10} CFU/mL from Test 1 using corresponding time points).
- e. The SS will be considered non-toxic if the mean \log_{10} CFU/mL of Test 2 is not more than 0.20 \log_{10} less than the mean \log_{10} CFU/mL of Test 3 (Mean \log_{10} CFU/mL from Test 3 – Mean \log_{10} CFU/mL from Test 2 using corresponding time points).
- f. All sterility controls must be negative for growth.
- g. The amount of CFU added for each aspect must be confirmed to yield a final suspension containing approximately 30-100 CFU/mL (validated in Test 3).

Controls:

Sterility Control

Duplicate plates of TSA and TSA+ used will be incubated with the test. In addition, duplicate 1.0-mL aliquots of SS and PBW will be plated using TSA pour plates. All plates will be incubated with the test plates.

Challenge microorganism confirmation:

Visually confirm the morphology characteristics of both the test organisms following all Tests with all products.

Protocol Number: MPS-17IPVAW10

Version: 1.0

Date: 05.25.17

Challenge microorganism Assays:

An initial assay confirming the amount of microorganism present will be performed prior to testing and a final assay will be performed to confirm the amount of microorganism present at the completion of the assay, pour plated in duplicate using TSA.

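### Neutralizer validation Test 1 plates no uninoculated skin sample, so surviving skin flora could turn a failing result into a pass

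*Protocol*

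**What the plan says.** Protocol 10.3.5 requires the neutralizer system to be validated before the study starts, "to demonstrate that the antimicrobial is effectively neutralized and there is no effect on the growth of microorganisms". Appendix 22.8 gives the procedure.

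- **Sample.** Volunteers' abdominal skin is wiped for one minute with 70% isopropyl alcohol, treated with the test article, and sampled by scrub cup at about 10 minutes. For Test 1, "Out of the 6.0 mL aliquot of SS taken from the volunteer, 4.90 mL will be transferred to a new sterile tube" and 0.1 mL of a *Staphylococcus epidermidis* suspension is added.
- **Counting.** "Duplicate one mL aliquots will be removed and plated using TSA pour plates", within one minute and again after 30 minutes, in four replicates per organism. The interpretation rules equate the number of surviving challenge organisms with the average of the duplicate plate counts.
- **Pass rule.** The Test 1 mean may be at most 0.20 log10 below the Test 3 mean. Nothing limits how far it may lie above.
- **Controls.** The uninoculated plates are TSA, TSA+, sampling solution and buffered water. Colony morphology is confirmed by eye.
- **Incubation.** In the validation, "All plates for Tests 1, 2, 3 and 4 will be incubated for 48 ± 4 hours at" 35 ± 2 °C. Trial samples go on TSA+ (agar with neutralizers), and 10.3.5 states: "After 72 ± 4 hours of aerobic incubation at 30 ± 2C, colonies will be counted".

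SAP 3.3 leaves the neutralization analysis to the clinical site.

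**The concern.** Test 1 fluid comes from skin and may carry native bacteria. TSA is non-selective, and the count has no step that separates challenge colonies from flora. Because the pass rule looks in one direction only, every extra colony moves Test 1 towards passing. The liquids plated without inoculum show that the reagents are sterile; they say nothing about what the skin sample brought in.

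The stake is the meaning of a pass. The validation is there to show that residual octenidine in a sample does not go on suppressing bacteria after collection. Such carry-over would lower post-treatment counts in the investigational arm and not in the controls, and so would favour the product in the comparison with the 1.2 log10 margin. A validation that flora can push over the line gives weaker assurance than its 0.20 log10 limit suggests.

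**Working it through.** **Inputs.** From Appendix 22.8: 4.90 mL sample plus 0.10 mL inoculum (5.0 mL in the tube); inoculum titer 1.5 × 10³ to 5.0 × 10³ CFU/mL; limit 0.20 log10; four replicates with duplicate 1 mL plates. From 10.3.5: 6 mL of sampling solution over 3.46 cm². Assumed, because the documents give no figure: the size of the loss, the residual flora, and whether flora are inhibited.

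**The plan's own figure.** 1.5 × 10³ × 0.1 / 5.0 = 30 CFU/mL, and 5.0 × 10³ × 0.1 / 5.0 = 100 CFU/mL. This reproduces the stated 30–100 CFU/mL.

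**What the rule tolerates.** 10^(−0.20) = 0.631, so without flora a loss of up to 36.9% passes. A 50% loss is 0.30 log10 and should fail.

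**Flora needed to mask a loss.** Let N be the challenge density, L the fraction lost and b the flora density in the tube before any inhibition, in CFU/mL. On skin this is b × (5.0/4.9) × (6/3.46) = 1.77 b CFU/cm².

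- (a) Flora unaffected: (1 − L)N + b ≥ 0.631N. For L = 0.5, b = 0.131N, which is 3.9 CFU/mL at N = 30 and 13.1 at N = 100.
- (b) Flora inhibited equally: (1 − L)(N + b) ≥ 0.631N. For L = 0.5, b = 0.262N, which is 7.9 CFU/mL at N = 30 and 26.2 at N = 100.

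Residual flora needed, in CFU/cm²:

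| Loss | (a) N = 30 | (a) N = 100 | (b) N = 30 | (b) N = 100 |
|---|---|---|---|---|
| 50% | 7.0 | 23.2 | 13.9 | 46.3 |
| 90% | 28.2 | 94.0 | 282 | 940 |
| 100% | 33.5 | 111.6 | cannot be masked | cannot be masked |

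**With counting noise.** Poisson simulation of the pass rule: 50% loss, case (a), four replicates of two plates, 40,000 runs. Probability of passing:

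| Residual flora | N = 30 | N = 65 | N = 100 |
|---|---|---|---|
| none | 0.015 | 0.001 | 0.000 |
| 1.0 log10/cm² | 0.793 | 0.148 | 0.015 |
| 1.5 log10/cm² | 1.000 | 0.999 | 0.899 |

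Without flora the rule does its job. With about 32 CFU/cm² it mostly does not.

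**Against the only flora figure given.** Appendix 22.8 puts normal skin at 10² to 10⁵ CFU/cm². The 50% thresholds in case (a) are 0.84 to 1.36 log10. Starting from 10², enough flora remain if alcohol plus product remove less than 2 − 1.36 = 0.64 log10 (N = 100) or 2 − 0.84 = 1.16 log10 (N = 30). Starting from 10⁵, the figures are 3.64 and 4.16 log10. The documents do not give the reduction achieved.

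**Material for a control.** 6.0 − 4.9 = 1.1 mL is left with no stated use: enough for one 1.0 mL plate per replicate, not a duplicate.

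**The case against.** The strongest reply is that the flora may simply not be there. The skin is wiped with alcohol and then scrubbed with the product for three minutes. The volunteers are exempt from the 72-hour bathing restriction and from any minimum count, so they may start low. The interpretation rule speaks of challenge organisms, and morphology is checked by eye. If flora are as sensitive as the challenge organism, the density needed doubles for a 50% loss and total failure cannot be hidden. All of this stands and lowers the risk. It does not remove it: no residual count is taken, the morphology check has no exclusion or subtraction rule, and the challenge organism is itself a skin staphylococcus that native colonies may resemble.

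The documents do not support several stronger readings that a reader might infer:

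- *The trial's recovery system is untested.* The sampling solution, scrub-cup sampling and 30-minute hold are all tested. What is never challenged with an organism is TSA+ at 72 h and 30 °C.
- *The agar and incubation differences favour the investigational product.* Plain TSA is the harder condition for showing neutralization. Toxicity of TSA+ would act on all three arms; a proportional loss cancels in the log10 difference, and the floor of 1 CFU/cm² could only shrink the product's effect.
- *A masked 50% loss inflates the trial effect by 0.30 log10, a quarter of the 1.2 margin.* That loss would be seen on neutralizer-free agar, whereas trial plates contain neutralizers. The rule also already accepts 0.20 log10 without any flora, so masking this case lets through a further 0.10.
- *The validation is the only safeguard.* Neutralizers in the sampling solution and the agar, serial dilution and plating within 30 minutes are safeguards too; the validation checks neutralization.

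**Conclusion.** The concern holds as a gap in one control. Test 1 as written cannot distinguish adequate neutralization from partial carry-over offset by surviving flora, and the one-directional rule makes every such error a pass. For a 50% loss, the flora needed are about 7–23 CFU/cm² (unaffected) or 14–46 CFU/cm² (equally inhibited) over the 30–100 CFU/mL challenge range. These figures rest on an assumed loss and an unstated residual level. The documents do not show that masking would occur, nor that trial results would be biased. It is a cheap improvement, not a defect that undermines the study. The absence of any challenge on TSA+ under trial incubation is a secondary point and not a source of bias towards the product.

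**What to change.** In Appendix 22.8, Test 1:

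1. Plate 1.0 mL of the unused 1.1 mL from each replicate without inoculum, on the same agar and incubation as Test 1.
2. Multiply that count by 0.98 (4.9/5.0) for the dilution by the inoculum, subtract it from the replicate's Test 1 count, and apply the 0.20 log10 rule to the corrected mean. State in advance how a corrected count of zero or less is handled.
3. Plate it with the first enumeration. One plate must serve both time points; if flora decline during the hold, it over-corrects at 30 minutes, which is the cautious direction.

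Cost: 4 replicates × 2 organisms = about eight plates, with no extra subjects or visits. A single plate adds counting noise: at 13.1 CFU/mL of background the Poisson SD is √13.1 = 3.6 per replicate, or 1.8 averaged over four. The plate also depends on the full 6.0 mL being recovered from the skin.

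If recovery on TSA+ is also to be shown, keep plain TSA for Tests 1 to 3 and add TSA+ plates at 72 h and 30 °C in parallel, with Test 3 on both agars. Replacing plain TSA would drop the stricter carry-over test, and with Test 3 on TSA+ alone any toxicity of that agar would cancel. The Test 3 set is 4 × 2 plates × 2 times × 2 organisms = 32 plates. The Test 1 tube has only 5.0 − 4 × 1.0 = 1.0 mL to spare, so it allows one TSA+ plate per replicate.

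If the validation is already complete, report the missing control, the media difference and any non-challenge colonies seen as limitations in the final report.

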22.9 Skin Irritation Rating Scale

Skin Irritation Rating Scale		
Reactive area(s) within the treatment site only		
Condition	Rating	Description
Erythema	0	No reaction
	1	Mild and/or transient redness
	2 ^a	Moderate redness
	3 ^b	Severe redness
Edema	0	No reaction
	1 ^c	Mild and/or transient swelling
	2 ^a	Moderate swelling
	3 ^b	Severe swelling
Rash	0	No reaction
	1 ^c	Mild and/or transient rash
	2 ^a	Moderate rash
	3 ^b	Severe rash
Dryness	0	No reaction
	1 ^c	Mild and/or transient dryness
	2 ^a	Moderate dryness
	3 ^b	Severe dryness

^a = Represents significant irritation in any category and may require subject's removal from the study.

^b = A rating of 3 on the skin irritation scale in any category will be recorded as Adverse Event and will require subject's removal from the study.

^c = If a subject receives a score of 1 for erythema, edema, rash, and/or dryness prior to baseline sampling on Treatment Day, they will be dismissed from testing that day, and can move to another group and participate once the irritation subsides.

**BD PROTOCOL # MPS-17IPVAW10
BIOSCIENCE LABORATORIES, INC., PROTOCOL #1704167-103**

**Protocol Title: A Randomized, Single-Center, Blinded, Clinical Evaluation of the
Antimicrobial Effectiveness of an Antimicrobial Cloth Compared to Vehicle and 0.9%
Saline**

Protocol Version: Version 1.0/05.25.17

ACCEPTED BY: BIOSCIENCE LABORATORIES, INC. (TESTING FACILITY)

[name]
[name]

Principal
Investigator:

[figure not shown]

[name], CCRP

06/01/2017
Date of Study Initiation

GIRB Approved
Date: 6-5-17
Initial: PL

Signature Page for MPS-17IPVAW10 Protocol 30May2017

Signature Page for MPS-17IPVAW10 Protocol 30May2017 - System Version No. 1.0

GIRB Approved
Date: 6-5-17
Initial: AK

For the average treatment effect correcting for pre-treatment log₁₀ bacterial counts, the per-protocol data may be different from the modified intent to treat (mITT) data and analysis will be made separately based on both the per-protocol data and the modified intent to treat (mITT) data if two data sets are different. Summary statements will be made for each analysis to show whether superiority of the Investigational Product as compared to the Vehicle Control and the Saline Control is satisfied. Links to tables showing analysis results will be provided.

3 Overall Study Description

3.1 Study Background

A Phase 2 study MPS-16IPVAW01 evaluated the antimicrobial efficacy of thermally treated polyester cloths impregnated with 0.4% w/v octenidine dihydrochloride in aqueous formulation as compared to the thermally treated polyester cloth impregnated with vehicle formulation and the FDA-approved active comparator SAGE 2% CHG cloth. Activity was assessed relative to a 70% response rate target based on the log reduction standards in the 1994 FDA TFM. The current study will evaluate the immediate antimicrobial efficacy of thermally treated polyester cloths impregnated with 0.4% w/v octenidine dihydrochloride in aqueous formulation as compared to two negative controls, the thermally treated polyester cloth impregnated with vehicle formulation and a polyester cloth containing 0.9% normal saline, according to the revised statistical analyses and expected performance criteria published by the FDA on January 19, 2017.

3.2 Objectives

3.2.1 Primary Objectives

The primary objective of this study is to compare the immediate antimicrobial activities of a thermally treated polyester cloth impregnated with 0.4% w/v octenidine dihydrochloride in aqueous solution to thermally treated polyester cloths impregnated with vehicle formulation and a polyester cloth containing 0.9% saline. In agreement with the Food and Drug Administration Tentative Final Monograph (TFM) for *Effectiveness Testing of a Patient Preoperative Skin Preparation*, a log reduction study will be used to determine antimicrobial efficacy based on the statistical analyses outlined in published letters from the FDA on January 19, 2017. Testing will be performed according to the procedures outlined in the Food and Drug Administration Tentative Final Monograph (TFM) for *Effectiveness Testing of a Patient Preoperative Skin Preparation* (FR 59:116, 17 June 94, pp. 31450-31452). The test methods for this evaluation will be based on ASTM Standard Test Method E1173-15, *Evaluation of Preoperative, Pre-catheterization, or Preinjection Skin Preparations* and the test criteria from the deferral letters published by the FDA on January 19, 2017.

At 10 minutes post-prep, the mean treatment effect of the test article vs. negative controls should be $> 1.2 \log_{10}$ on both the abdomen and the groin with 95% confidence. In this protocol two negative controls will be used, the Vehicle Control and the Saline Control.

3.2.2 Secondary Objectives

Safety will be evaluated using skin irritation scores and the incidence of adverse events.

3.3 Study Design

This single site study is a randomized, blinded design employing a minimum of 36 healthy volunteers, where each subject receives two of the planned treatments on the abdomen and groin.

Treatment materials for the following treatment groups will be blinded with treatment codes A or B:

- Thermally treated cloth impregnated with 0.4% w/v octenidine dihydrochloride aqueous solution (IP: Investigational Product).

- Thermally treated cloth impregnated with vehicle formulation (VC: Vehicle Control).

The 0.9% Saline Control (SC) cannot be blinded due to product application requirements and will be assigned to treatment code C.

Out of the minimum 36 evaluable subjects, 12 subjects will receive treatments from both A and B, 12 subjects will receive treatments from both A and C, and 12 subjects will receive treatments from both B and C to achieve 24 test sites from A, B and C for groin and abdominal regions. The application will be randomized so that each treatment is applied on an equal number of left and right sides of the body. Due to baseline requirements the final data set may be imbalanced with regard to right and left sides upon achieving the minimum number of qualifying body sites.

Subjects will be sampled for treatment day baseline microbial populations on randomly assigned sites of the abdominal and inguinal areas on both sides. Subjects will have samples collected at baseline and 10 minutes (± 30 seconds) on both abdomen and inguinal sites. All sampling times will be calculated from the completion of the dry time of each product following application.

There is a neutralization test before the main treatment study. Note: this statistical analysis plan is only for the Main Treatment study and does not include the analysis for the Neutralization study. The analysis for the Neutralization study will be conducted by the clinical site and included in the final clinical report.

The group treatments and number of treatment sites planned for each group for the main treatment study are shown in Table 1.

Table 1: Group treatments and number of treatment sites planned

Arm	Treatment	Number of evaluable treatment sites per anatomical site
Investigational Product (IP)	Thermally treated polyester cloth impregnated with 0.4% w/v octenidine dihydrochloride	24
Vehicle Control (VC)	Thermally treated polyester cloth impregnated with vehicle formulation	24
Saline Control (SC)	0.9% normal saline applied with polyester cloth	24

